4.2. General research methodology

The research has the following characteristics:

- Open study,
- Monocentric (CHD Vendée)
- Controlled,
- Superiority,
- Randomized

[figure not shown]
Inclusion period: 18 months

Participation period: 7 days

Research duration: 19 months maximum

Number of patients to be randomized: 50

4.3. *Study diagram*

4.4. Description and justification of the therapeutic regimen/method studied

The aim of the study is to evaluate the effect of wearing non-slip socks on motor recovery. We have therefore chosen a design where we will be able to evaluate the evolution of motor skills between a control group and the experimental group wearing the socks.

The non-slip socks used in this study (Appendix 3) will be those used in normal practice in our care department.

These socks from *CA Diffusion* feature picot strips on the outer 2 sides for continuous grip, even when the sock is turned. They have a resistant interior to keep out the cold. They are latex-free to prevent allergies.

Socks are changed every day to ensure good foot hygiene. They will be changed by the medical staff at the patient's bed.

4.5. Description of evaluation and data collected

4.5.1. Walking speed

Walking speed is a common physiotherapy test used to assess motor function. It is easy to use, even for patients with cognitive and confusional disorders. Gait speed in patients over 80 years of age is 0.943m/seconds \pm 0.091 (Bohannon & Williams Andrews, 2011; Menant et al., 2014)

The best initial estimates of small significant changes are close to 0.05 m/s for walking speed. (Perera et al., 2006)

Substantial changes are of the order of 0.10 m/s (Perera et al., 2006).

There are several ways of performing the test, at usual walking speed or at fast walking speed. For the purposes of this protocol, we have chosen the patient's preferred walking speed modality (Bohannon & Williams Andrews, 2011).

Ground markings or studs provide visual cues for the patient. The patient stands facing the 10m course, with visual cues to remind him or her of the course.

The walking speed test will be performed twice. The instructions are :

"At my starting marker, you'll have to walk at your usual speed to pass the marker".

"Are you ready?"

4.5.1. Double-task walking speed

Double-task walking speed gives an indication of available cognitive reserve (Lundin-Olsson et al., 1997). Stopping walking or reducing walking speed by more than 30% is predictive of a fall (Beauchet & Berrut, 2006).

Ground markings or studs provide visual cues. The patient stands facing the 10m course, with visual cues to remind him or her of the course.

The walking speed test will be performed twice. The instructions are :

"At my starting signal, you'll have to walk at your usual speed to pass the marker/plot on the ground. During this walk, you must name as many animals as possible.

"Are you ready?"

4.5.2. Imagined walking speed

Human movement can be separated into 2 phases, a programming phase (anticipation) and an execution phase (Jeannerod, 2001). The concordance between movement planning and execution can be reliably assessed using a simple test evaluating the temporal concordance between an imagined practice and a physical practice (Guillot et al., 2012). This concordance is expressed by an Isochrony Index. Adapted to imagined walking speed, this is a simple test designed to assess motor prediction abilities (Rulleau et al., 2015). Interestingly, the decrease in isochrony correlates with the decrease in gait speed during the dual task (Bridenbaugh et al., 2013)). It could thus mark a risk of falling due to poor anticipation of actual motor abilities.

Ground markings or studs provide visual cues. The patient stands facing the 10m course, with visual cues to remind him or her of the course.

The imagined walking speed test is performed twice. The instructions are "At my starting signal, you'll have to imagine yourself walking at your usual speed to pass the marker/plot on the ground. When you imagine passing it, you'll say "stop". "Are you ready?"

4.5.3. Fear of falling (Appendix 2)

The Short-Falls Efficacy Scale International (Short-FES-I) is a patient-completed self-questionnaire comprising 7 items with 4 possible answers. It has excellent internal consistency (Cronbach's alpha = 0.96 and 0.92) and test-retest reliability (ICC = 0.96 and 0.83). The convergent construct validity of the Short-FES-I was confirmed for: previous falls; depressive symptoms; general disability; low quality of life; and physi-caloric impairment (Dewan & MacDermid, 2014).

A threshold for fear of falling has been defined as > 10 on the Short-FES-I scale (Dewan & MacDermid, 2014).

4.5.4. The presence of a fall

The occurrence of a fall during hospitalization, the time of the fall and its consequences, and the total number of falls during the hospital stay will be recorded.

Falls and dates of falls prior to hospitalization of less than 6 months will also be collected.

4.5.5. Confusion Assesment Method (appendix 3)

This tool is designed to be used by healthcare personnel, who search for 4 groups of clinical signs (Haute Autorité de Santé, 2009; Kharat & Simonet, 2013) :

1. Sudden onset and fluctuating symptoms;
2. Inattention;
3. Disorganized thinking ;
4. Impaired alertness.

Diagnosis requires the presence of 3 of the 4 criteria. Criteria 1 and 2 are always required, along with 3 or 4 (Laplante & al, 2005,. Appendix 3).

4.5.6. Visual Analog Fatigue Scale

The visual analog scale is commonly used in pain assessment (Hawker et al., 2011). In addition, other authors propose its use in fatigue assessment, using the same modality (Hewlett et al., 2011)..

The slide is presented to the patient as follows:

"I'm going to ask you to move the slider to your current level of fatigue. I'm going to ask you to move the cursor to your current level of fatigue".

The operator rates fatigue from 0 to 100.

4.5.7. Length of stay

The length of stay in days and hours in geriatric short-stay or post-emergency medicine, calculated between the start of hospitalization and the end of hospitalization, will be recorded.

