1.2. Benefits and risks for research subjects

1.2.1. Benefits

1.2.1.1. *Individual profit*

Improved motor control
Improved practices with the use of non-slip socks

1.2.1.2. *Group profit*

Improved motor care for senior citizens, at a lower cost to society thanks to a shorter length of stay,
Improved motor management for faster discharge

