2.2. Objectives and secondary endpoints

2.2.1. Secondary objective(s)

1. Assessing the impact of anti-slip socks on short-term motor skills
2. Evaluate the impact of anti-slip socks on motor planning in the short term and during hospitalization
3. Evaluate the impact of wearing socks on dual-task abilities in the short term and during hospitalization
4. Evaluate the evolution of fear of falling with the use of socks in the short term and during hospitalization.
5. Evaluate the impact of socks on the presence of fall(s)
6. Length of stay in geriatric care or post-emergency medicine

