2.2.2. Secondary endpoints

1. Change in 10m walking speed between D1 (start of physiotherapy treatment) and D1' ("after a 3-minute walk with the shoe assigned following randomization"),
2. Evolution of isochrony between the speed of walking actually performed and the speed of walking imagined over 10m at D1, D1' and D8. The mean of two tests of each modality will be used.
3. Evolution of isochrony between walking speed and double-task walking speed over 10m at D1,D1' and D8 (Beauchet et al., 2010; Menant et al., 2014). The mean of two tests of each modality will be used.
4. Total score > 10 on the Short-Falls Efficacy Scale International questionnaire at D1, D1' and D8
5. Presence of fall(s) and their consequences during hospitalization
6. Length of stay calculated from start of hospitalization to end of hospitalization

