4.7. Rules for terminating a person's participation

4.7.1. Criteria for premature termination of a person's participation in research

A person's participation may be terminated prematurely for the following reasons:

- Withdrawal of consent by the patient

Patients will be able to withdraw their consent and ask to leave the study at any time, for any reason.

- Death.

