6.2.1. Description of planned statistical methods, including schedule of planned interim analyses

All variables will be described globally and by group. The description will include the number and percentage of modalities for qualitative variables, and the minimum, maximum, mean, standard deviation and median for quantitative variables.

All gait speed criteria, isochrony between imagined and executed gait speed, isochrony between normal gait speed and double-task gait will be compared using linear models taking into account the baseline J1 value.

As the evaluation conditions between D1' and D8 are different, the models evaluating evolution at D1' and D8 will be independent.

Fear of falling will be assessed using the Falls Efficacy Scale International questionnaire. Fear of falling is defined with a cut-off score equal to 10 on this questionnaire.

The number and percentage of patients with a fear of falling will be presented and compared at D1' and D8 using a Chi2 test.

Length of stay will be compared using a Student's t test.

The presence of falls and their consequences will be described during the hospital stay.

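### The end of the length-of-stay clock is inconsistent and death and transfer are not handled, so an in-hospital death can count as a short, favourable stay

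*Combined protocol and SAP*

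**What the plan says.** Length of stay is the sixth secondary objective and endpoint, and its end is described in two ways.

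- **Unit stay.** Objective 6 in section 2.2.1 reads "Length of stay in geriatric care or post-emergency medicine". The study schedule in 4.1.5 labels the item in the same way and places it in the hospital-discharge column, where it is the only entry. Section 4.5.7 opens with "The length of stay in days and hours in geriatric short-stay or post-emergency medicine".
- **Hospitalization.** Endpoint 6 in section 2.2.2 reads "Length of stay calculated from start of hospitalization to end of hospitalization". The sentence in 4.5.7 ends with "calculated between the start of hospitalization and the end of hospitalization, will be recorded".

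Section 6.2.1 gives the analysis: "Length of stay will be compared using a Student's t test". Section 6.2.7 bases the main analysis on all randomized patients. Section 1.2.1.2 states which direction is favourable: "at a lower cost to society thanks to a shorter length of stay" and "Improved motor management for faster discharge".

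Death appears in section 4.7.1, in the list introduced by "A person's participation may be terminated prematurely for the following reasons". No section says how a death or a transfer enters length of stay, and the imputation rule in 6.2.5 covers only the primary endpoint.

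**The concern.** A short stay is a good outcome only if it ends in the way the plan has in mind, which section 1.1.2 describes as an easier and earlier return home. Raw duration does not distinguish that from a stay cut short by death or, on one reading, by a move to another department. Patients are aged 75 or over on acute wards, and falls are one of the outcomes studied, so such events are foreseeable.

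If one arm had more of them, its mean stay could fall and be read as earlier discharge. The definition also leaves a choice to whoever enters or cleans the data, in an open trial, for every patient who changes department before leaving hospital.

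**Working it through.** **1. The plan's own figures.** No mean, standard deviation or target difference is given for length of stay, so there is no figure to reproduce for this endpoint. The stated total of 46 concerns walking speed: a difference of 0.10 m/s with SD 0.10, 5% two-sided and 90% power in a two-sample t test give 22.02 per arm, rounded up to 23, and 2 × 23 = 46. It does not bear on this point. The 50 patients randomized 1:1 (4.2, 6.2.8) give 25 per arm.

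**2. What each reading does with each event.**

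| Event | Unit stay (2.2.1, schedule, start of 4.5.7) | Hospitalization (2.2.2, end of 4.5.7) |
|---|---|---|
| Discharged home from the unit | Stay ends | Stay ends, same value |
| Moved to another department of the hospital | Stay ends at the move | Stay continues; added hospital time lengthens it |
| Death in the unit | Stay ends at death | Stay ends at death, same value |

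The readings disagree on transfers and agree on death. If, as an assumption, a transferred patient spends 10 more days in hospital, the two definitions differ by 10 days for that patient, or 10/25 = 0.4 day in the arm mean.

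**3. What the analysis does with a death.** There are two possibilities and the plan does not choose between them.

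- The duration up to death is entered. All randomized patients are analysed, and the t test treats the value like any other short stay.
- The value is left missing, because death ends participation (4.7.1) and the item is collected at discharge. No rule for missing length of stay exists, so the patient drops out and the comparison is made among survivors.

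**4. Size, on assumed inputs.** Suppose patients without an event stay m days on average, and k extra patients in one arm have a recorded stay cut to d days. The shift in that arm's mean is k × (m − d) / 25. The documents give neither m nor d; I take m from 10 to 14 and d from 3 to 6.

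- Smallest, one event: (10 − 6)/25 = 0.16 day.
- Largest, one event: (14 − 3)/25 = 0.44 day.
- Three extra events: 3 × 0.16 = 0.48 to 3 × 0.44 = 1.32 days.

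If both arms have the same number of events at similar times, the shifts cancel in the difference.

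**5. Against the noise.** With an assumed SD of 4 to 7 days, the standard error of the difference is SD × √(2/25): 4 × 0.283 = 1.1 days to 7 × 0.283 = 2.0 days. The difference detectable with 80% power (two-sided 5%) is 3.2 to 5.7 days. Even the most extreme combination above, 1.32 days against a standard error of 1.13, is 1.32/1.13 = 1.2 standard errors.

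**The case against.** The strongest reply is that the plan is being read uncharitably. Endpoint 6 and the closing words of 4.5.7 both run the clock to the end of hospitalization. On that reading a move to another department does not end the stay, and an injurious fall would tend to lengthen it, which is unfavourable. This stands. A reader might infer from the opening words of 4.5.7 that the clock always stops on leaving the unit, and so that injurious falls improve the endpoint. The documents do not support that as a general statement; it follows only on the unit reading.

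The second reply is that nothing says a death is scored as a short stay. Sections 4.7.1 and 4.7.2 end participation and further data collection, so a death might be left missing. This also stands: scoring it as short is what the wording allows, not what it prescribes. But the missing-value alternative has no rule either, so the gap remains.

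Third, a reader might infer that deaths appear in no outcome and that the reason a stay ended is lost. That is too strong. Falls, their timing and consequences are recorded (4.5.4) and described (6.2.1). Reasons for missing data are described by group (6.2.5), so a death before D8 should surface. Monitors have access to medical and nursing records (7.3). What is absent is a planned field and an analysis that links these events to length of stay.

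Finally, a unit stay is a legitimate target if the sponsor wants one, and the endpoint is secondary. Both are fair. The first would still require one consistent definition and a rule for death.

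**Conclusion.** The point holds for the inconsistent end of the clock and for the missing rule on death. It holds for transfers only if the unit reading is used. The possible distortion runs in the direction that section 1.2.1.2 calls a benefit, and needs an imbalance in events between arms. The size, 0.16 to 0.44 day in an arm's mean per extra event, rests on assumed mean stays of 10 to 14 days and events on days 3 to 6; none of these inputs comes from the documents. A few events would bias the estimate but are unlikely to produce a significant result alone. The primary endpoint and the sample size are unaffected. The change is worth making because it is cheap and because length of stay is part of the plan's stated case for benefit.

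**What to change.** 1. Use one definition in 2.2.1, 2.2.2, 4.5.7 and the schedule: time from the start of hospitalization to live discharge, continuing across transfers within the hospital.
2. Add reason for end of stay and destination to the discharge column (for example home, institution or rehabilitation, another acute department, death). Both can be taken from the medical record.
3. In 6.2.1, replace the t test on raw duration with a comparison that does not reward death. One option is a rank-based test with in-hospital deaths ranked as the longest stay; another is an analysis of live discharge with death as a competing event. Name one before the data are seen.
4. Report deaths and transfers by arm beside the description of falls.

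The cost is a few sentences and one discharge item, with no change to recruitment or to the sample size. The downside is that the result is reported as ranks or medians (or, with the competing-event option, as a comparison of live discharge over time) and not as a simple difference in mean days.

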4.6. Identification of all source data not contained in the medical record

1. Confusion Assesment Method scale	at D1
2. Visual Analogue Fatigue Scale	at D1, D1' and D8
3. Type of technical aid(s)	at J1, J1', J8
4. Duration of 10 m walk (2 times) performed	at D1, D1' and D8
5. Duration of double-task 10 m walk (2 times) performed	at D1, D1' and D8
6. Duration of imagined 10 m walk (2 times) performed	at D1, D1' and D8
7. Short-Falls Efficacy Scale International questionnaire	at D1, D1' and D8

4.7. Rules for terminating a person's participation

4.7.1. Criteria for premature termination of a person's participation in research

A person's participation may be terminated prematurely for the following reasons:

- Withdrawal of consent by the patient

Patients will be able to withdraw their consent and ask to leave the study at any time, for any reason.

- Death.

4.7.2. Monitoring and data collection schedule

Patients withdrawn from the study will not continue in the study schedule.

In the event of withdrawal of consent by the patient, and without prejudice to the patient's rights, the data already collected will be analyzed in accordance with regulatory texts.

However, no other tests specifically provided for in the protocol will be carried out, and no data will be collected.

Discharging a patient from the study program will in no way change his or her usual management of his or her pathology.

4.7.3. Criteria for discontinuing all or part of a research project (excluding biostatistical considerations)

Part or all of the study may be stopped permanently or temporarily by decision of the ANSM, the CPP and/or the study Sponsor.

In all cases :

- A written confirmation will be sent to the investigator coordinating the study (specifying the reasons for premature termination)
- All patients in the study will be informed.

4.7.4. Patient management at the end of the research study

Patients will be cared for according to the department's usual practices.

4.8. COMPENSATION

No compensation is provided for participation in this study.

5. SAFETY ASSESSMENT

As the study corresponds to a category 2 RIPH (Research Involving the Human Person), the applicable vigilance measures are those put in place for the practice of care and the use of products associated with the study, in accordance with article L1123-10 of the French Public Health Code. The investigator will therefore be responsible for reporting the occurrence of any undesirable event, in accordance with the procedures applicable to the CHD Vendée.

6. DATA MANAGEMENT AND STATISTICS

6.1. Study data collection and processing

6.1.1. Data collection

An observation notebook (eCRF) will be created for each patient. All information required by the protocol must be provided in the eCRF. It must include the data needed to confirm compliance with the protocol and all the data required for statistical analysis; it must also enable major deviations from the protocol to be identified.

The person(s) responsible for filling in the eCRFs (investigator, CRA, etc.) must be defined and is/are identified in the task delegation form (kept in the investigator's folder).

At the end of the study, the investigator will sign the eCRFs to certify the conformity of the data collected.

6.1.2. Data coding

By signing this protocol, the principal investigator/qualified person and all the members of his or her team undertake to keep confidential the identities of the patients who have participated in the study.

The transmission of a person's data for research purposes will therefore only be possible if a coding system is used, and the presentation of research results will exclude any direct or indirect identification.

Patients will be identified in order of inclusion by a number automatically assigned by the Ennov Clinical software (eCRF), then completed by the patient's initials (1st letter of first name + 1st letter of last name).

This code will be the only information on the eCRF that can be used to link the eCRF to the patient.

The investigator/qualified person is also required to code patient data on any documents he/she may have in his/her possession which are attached to the eCRF.

A correspondence table will be set up at the participating center. This table will be kept in a secure place by the principal investigator/qualified person at the center, and will contain the patient code and nominative data, so that it can be traced back to the patient file in the event of missing or erroneous data. No clinical data will be collected in these correspondence tables.

6.1.3. Data processing

The collection of clinical data will be based on the creation of a database and data entry masks similar to the observation book, in compliance with the protocol and regulations currently in force.

6.2. *Statistics*

Software

Analyses will be performed using R software version 3.5.1

6.2.1. Description of planned statistical methods, including schedule of planned interim analyses

All variables will be described globally and by group. The description will include the number and percentage of modalities for qualitative variables, and the minimum, maximum, mean, standard deviation and median for quantitative variables.

All gait speed criteria, isochrony between imagined and executed gait speed, isochrony between normal gait speed and double-task gait will be compared using linear models taking into account the baseline J1 value.

As the evaluation conditions between D1' and D8 are different, the models evaluating evolution at D1' and D8 will be independent.

Fear of falling will be assessed using the Falls Efficacy Scale International questionnaire. Fear of falling is defined with a cut-off score equal to 10 on this questionnaire.

The number and percentage of patients with a fear of falling will be presented and compared at D1' and D8 using a Chi2 test.

Length of stay will be compared using a Student's t test.

The presence of falls and their consequences will be described during the hospital stay.

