4. DESIGN AND STUDY PROCESS

4.1. Study schedule

4.1.1. Inclusion and baseline tests (J1)

Patients arrive on the ward and are assessed by the doctor, who prescribes physiotherapy if necessary.

The physiotherapist takes note of the prescription on the first working day thereafter. The physiotherapist carries out a routine analysis of the patient's footwear. If the footwear is unsuitable, or if the patient is barefoot, the physiotherapist checks the patient's eligibility criteria. If the patient meets these criteria, he or she is informed of the study. If the patient gives oral consent, the physiotherapist will perform the Baseline tests (D1).

Baseline: J1 tests

The physiotherapist assesses the patient during the first diagnostic session, and performs the *Confusion Assessment Method* if it has not been done in routine practice.

A Visual Analogue Fatigue Assessment will be carried out prior to clinical testing.

For research purposes, the J1 tests will be performed barefoot:

1. Patient's walking speed over 10 m (2 times)
2. Walking speed in dual-task situation over 10 m (2 times)

Two other less common but validated assessments in this population will be carried out.

3. Imagined walking speed over 10 m (2 times)

The average of each of the two tests will be used for items 1 to 4.

Together, these tests take the patient around 10 minutes.

4. Short-Falls Efficacy Scale International Questionnaire

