4.1.3. J1' follow-up

After these 3 minutes of walking with or without the socks, depending on the randomization arm, and in order to assess the immediate effect of wearing anti-slip socks on motor skills, the patient will perform the same tests as on D1, in the same order.

A Visual Analogue Fatigue Assessment will be performed prior to the following clinical tests:

1. Patient's walking speed over 10 m (2 times)
2. Walking speed in dual-task situation over 10 m (2 times)
3. Imagined walking speed over 10 m (2 times)

The tests will be carried out by the patient with bare feet (control arm) or with non-slip socks (experimental arm).

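### Fear of falling (secondary objective 4) is tested only by an unadjusted Chi2 on the share above the cut-off; adding a D1-adjusted comparison of the Short-FES-I total score would be a cheap improvement

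*Combined protocol and SAP*

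**What the plan says.** All references are to the combined protocol and SAP.

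- **Objective.** Section 2.2.1, item 4: "Evaluate the evolution of fear of falling with the use of socks in the short term and during hospitalization".
- **Endpoint.** Section 2.2.2, item 4, makes it binary: "Total score > 10 on the Short-Falls Efficacy Scale International questionnaire at D1, D1' and D8". Section 4.5.3 gives the basis: "A threshold for fear of falling has been defined as > 10 on the Short-FES-I scale".
- **Test.** Section 6.2.1: "The number and percentage of patients with a fear of falling will be presented and compared at D1' and D8 using a Chi2 test". No baseline term is mentioned.
- **Other repeated measures.** In the same section, gait speed and the two isochronies "will be compared using linear models taking into account the baseline J1 value". Fear of falling is not in that list.
- **Description.** Section 6.2.1 also states that "All variables will be described globally and by group", so the total score can be summarised by arm without being tested.
- **Collection at D1 and D8.** The questionnaire is item 4 of the D1 list in 4.1.1 ("Short-Falls Efficacy Scale International Questionnaire") and item 4 of the D8 list in 4.1.5. The schedule table marks it at J1 and J8.
- **Collection at D1'.** Sections 2.2.2, 4.6 and 6.2.1 expect it. Section 4.1.3 says that "the patient will perform the same tests as on D1, in the same order", but its own list stops after the three walking tests, and the schedule table has no mark at J1'.

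**The concern.** The objective is about change. The test compares status at one time point, on a yes/no version of a 7-item score. It uses neither each patient's starting level nor any movement that does not cross the cut-off. A patient who improves by several points but stays above 10 counts as unchanged.

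With 25 patients per arm this can cost power that the data already scheduled at D1 and D8 could recover. At stake is how informative the answer to objective 4 will be. The primary endpoint is not involved.

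A second, separate issue concerns D1'. If the questionnaire is not given there, one of the two planned Chi2 tests has no data and the short-term half of objective 4 goes unanswered.

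**Working it through.** **1. The plan's own figure.** Section 6.2.2 assumes a difference of 0.10 m/s, SD 0.10, alpha 5% and power 90%. The standardised difference is 0.10/0.10 = 1.0. A two-sided two-sample t test needs 22.02 per arm, so 23 per arm, 46 in total, as stated. The normal approximation, 2 × (1.960 + 1.282)² = 21.0, gives 22 per arm (44). The 46 is reproduced. It applies to gait speed only; no power is claimed for fear of falling.

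**2. Inputs for fear of falling.** From the documents: 50 randomized 1:1, so 25 per arm; 7 items with 4 answers each; cut-off > 10. Assumed, because the documents do not give them: items scored 1–4 (range 7–28), mean, SD, effect size and shape, D1–D8 correlation ρ, two-sided 5%, and everyone assessed at D8.

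**3. Formula check, ignoring rounding and floor (effect d = 0.5 SD).**

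- *Chi2*, with 70% of controls above the cut-off. A 0.5 SD shift gives 51% in the sock arm. Pooled SE = √(2 × 0.605 × 0.395/25) = 0.138; unpooled SE = √((0.70 × 0.30 + 0.51 × 0.49)/25) = 0.136. Power = Φ((0.19 − 1.96 × 0.138)/0.136) ≈ 28%. With 50% and 85% of controls above the cut-off it is 28% and 23%.
- *Score adjusted for D1*. The noncentrality is d/√(1 − ρ²) × √(25/2). For ρ = 0.3, 0.5, 0.7 and 0.8 this is 1.85, 2.04, 2.47 and 2.95, giving power 44%, 52%, 68% and 82%.

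**4. Simulation with an integer score bounded at 7–28.** 20,000 trials per scenario, uniform shift of 0.5 SD, Chi2 without continuity correction. Power in %:

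| Control mean/SD (share > 10) | Chi2 | Score, ρ = 0.3 | ρ = 0.5 | ρ = 0.7 |
|---|---|---|---|---|
| 9/4 (35%) | 26.1 | 35.5 | 40.7 | 51.1 |
| 10/4 (45%) | 29.6 | 37.9 | 43.6 | 56.3 |
| 12/4 (65%) | 32.4 | 40.9 | 46.9 | 62.5 |
| 12/5 (62%) | 32.6 | 39.7 | 45.3 | 60.2 |
| 15/5 (82%) | 26.2 | 42.5 | 49.0 | 63.8 |

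Repeat runs agree to within about one percentage point. At ρ = 0.8 the adjusted score reaches about 65–78%. Other effect sizes:

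- 0.3 SD: Chi2 13–16%; the gain is 2–7 points at ρ = 0.3, 4–9 at 0.5 and 10–17 at 0.7.
- 0.8 SD: Chi2 52–66%; the gain is 12–22, 18–29 and 28–38 points.

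**5. Where the gain comes from (0.5 SD).** Using the score instead of the cut-off gives 5–14 points. Adding the D1 score gives a further 1–2 points at ρ = 0.3, 6–9 at 0.5 and 17–24 at 0.7.

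**6. No effect.** The adjusted model rejects about 5% of the time and the uncorrected Chi2 about 5–7%. Section 6.2.1 does not say whether a continuity correction is used. With one, Chi2 power at 0.5 SD falls to about 15–23%.

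**7. A different effect shape.** Same five settings, but the effect is confined to patients just above the cut-off (assumed: D8 score between 10.5 and 15, of whom 60% drop 4 points). Chi2 power is then about 26–42%, against about 9–23% for the adjusted score at ρ = 0.3–0.7. The ranking reverses.

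**8. D1' and cut-off, side by side.** Questionnaire at D1' expected: 2.2.2, 4.6, 6.2.1 and, by its general sentence, 4.1.3. Omitted: the test list in 4.1.3 and the schedule table. The cut-off is > 10 in 2.2.2 and 4.5.3. Section 6.2.1 gives a cut-off of 10 without saying where a score of exactly 10 falls, and it leaves out the word Short from the scale's name.

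**The case against.** The strongest reply is that nothing here is an error. Endpoint 4 is defined as a score above 10, section 4.5.3 supplies the threshold, and section 6.2.1 tests exactly that. Section 6.2.2 powers only gait speed, so low power on a secondary endpoint breaks no promise, and the score will be described by arm anyway. All of this stands, and it is why the point is an improvement and not a fault. It does not close the gap between an objective about evolution and a test that ignores the starting level.

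Second, the power gain rests on assumptions, the main one being a uniform shift. This also stands: step 7 is deliberately extreme and no better grounded in the documents, but it shows that the gain depends on effect shape.

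Third, adjustment could do harm. Section 4.1.2 places randomization after the D1 tests and section 6.2.8 places it before them. The study is open and the Short-FES-I is self-reported. If allocation is known when D1 is completed, the D1 answers may be affected by it, and adjusting for them could introduce a bias that the unadjusted Chi2 avoids. This is a real condition on the fix.

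A reader might go further and infer any of the following, which the documents do not support:

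- *The Chi2 is biased or invalid.* It is a legitimate randomized comparison of the stated binary endpoint.
- *The score model is always more powerful.* Step 7 contradicts this.
- *Even the adjusted score must stay below some fixed power, such as 65% at 0.5 SD.* That depends on the correlation. Section 4.5.3 quotes test–retest ICCs of 0.96 and 0.83. These are not D1–D8 correlations in recovering inpatients, but they give no reason to stop at 0.7.
- *D1' data will certainly be missing.* The sections conflict; they do not settle it.

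**Conclusion.** The point holds as a low-cost improvement to one secondary analysis. The plan leaves an already collected score and its baseline out of every test of objective 4, while using the D1 value for the other repeated measures.

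Under a uniform 0.5 SD shift with 25 per arm, the D1-adjusted score raises power in every setting tried. The gain ranges from small at correlation 0.3 to large at 0.7–0.8. Score mean, SD, correlation, effect size and effect shape are all assumed, and complete D8 assessment is assumed too. Across much of that range power stays well below the 90% used for gait speed, so a non-significant result would often remain inconclusive.

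The benefit depends on two conditions: an effect not concentrated just above the cut-off, and a D1 score completed before allocation is known.

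The D1' inconsistency and the cut-off wording rest on the text alone and need reconciling whatever is decided about the model. The primary endpoint, its analysis and the 46/50 sample size are untouched.

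**What to change.** 1. **Reconcile sections 4.1.2 and 6.2.8** on whether the D1 assessments precede randomization. Adopt the adjustment only if D1 is completed before allocation is known. The same question bears on every D1-adjusted model, including the primary one.
2. **In 6.2.1, with a matching line in 2.2.2,** add a prespecified comparison of the D8 Short-FES-I total score, using the linear model already planned for gait and adjusted for the D1 score.
3. **Keep the proportion > 10 and its Chi2** for interpretation, and state in advance which of the two leads for objective 4.
4. **Separately, state whether the questionnaire is given at D1'.** Align 2.2.2, 4.1.3, the schedule table in 4.1.5, 4.6 and 6.2.1. If it is not given, delete the D1' comparison.
5. **Use one cut-off wording and one scale name** in 2.2.2, 4.5.3 and 6.2.1.

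Cost: a few lines of text and no new data at D8. If the change is treated as substantial, section 7.7 sends it to the ethics committee (CPP).

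Downsides: a linear model is approximate for a bounded score, although its simulated type I error was 4.7–5.2%. The documents give no meaningful difference for the total score, so the proportion is still needed. The precision gain is not guaranteed for every effect shape. Section 6.2.5 sets an imputation rule for the primary endpoint only, so handling of missing D8 questionnaires should be stated too.
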